In keeping with the recommendations of Foy and colleagues, Schnurr et al. (2003) examined the impact of Trauma-focused Group Therapy (TFGT) with 360 Vietnam veterans within the VA system (VA Cooperative 420 Study). TFGT involved groups of 6 male patients who met weekly for 30 weeks, followed by 5 booster sessions. Importantly, TFGT began ET slowly, waiting to introduce the technique until session 12. ET was conducted and shared within the group format (each group member listened to each others' exposure items). TFGT was compared with a Present-Centered Group Treatment (PCGT) that focused on current problems and avoided a trauma focus. Results indicated that patients in both treatment conditions showed improvements (average of 40% showing clinically significant change), although no difference was noted between the two interventions. Narrowing the analyses to veterans who had received

an adequate dose of treatment (at least 24 sessions) indicated that TFGT was marginally more efficacious in reducing avoidance and numbing symptoms and possibly overall PTSD symptom severity ( $p = .06$ ). Schnurr et al. (2003) discuss the role of in-session exposure in these outcomes, indicating that perhaps the “dosage” of ET was not sufficient in TFGT. In considering TFGT, it is notable that this treatment program is fairly long (30 sessions) and requires some degree of distress tolerance from veterans, given that ET was conducted within the group. Recently, Ready et al. (2008) presented data from an uncontrolled trial of Group Exposure Therapy, which is somewhat similar to TFGT; the pre-to-post effect size was 1.20 in a sample of veterans with combat-related PTSD. Although promising, these studies suggest that group-based treatments for PTSD warrant continued study.

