- To assess homework compliance, we will use the homework compliance form; for GCBT, this form was developed during the treatment development project. For SGP, a parallel form will be created. Therapists will rate the percentage of each homework assignment that each participant completes each week and provide a rating of homework quality, following Primakoff et al. (1986) and successfully used in other RCTs (e.g., Leung & Heimberg, 1996).
- To qualitatively measure participants' experiences of the two different kinds of group formats, 7 open-ended questions about their experience will be asked at the 1-month post-treatment assessment. Answers to these questions will supplement quantitative data. Responding to these questions will take 3-5 minutes, and answers will be written, not recorded.

**D.5. Follow-up:** In designing this RCT, it was important to demonstrate durability of changes following GCBT and SGP and so, included a follow-up interval. The patients will be assessed three times during a 1-year follow up interval (at 3-, 6-, and 12 months).

**D. 6. Between-site coordination:** We (Drs. [name], [name], and [name]) have worked effectively together over the past several years. Based on our collaborative work experience, we anticipate that our collaboration during the execution of the project will likewise be productive. We have collaboratively revised the GCBT treatment manual to be suitable for Veterans, organized the assessment battery to be used during pilot testing, and collected pilot data with two separate treatment groups. This section will delineate roles, including efforts designed to facilitate coordination between the PI's and the Co-I. In the initial months of the project, Drs. [name], [name] and [name] will write a procedures/operations manual. This manual will provide a detailed outline of each procedure, including recruitment procedures, each step in the assessment process, case management before and after treatment, specific procedures involved in treatment, and data management. The standardization of these procedures will ensure between-site coordination, as all personnel will have available a written set of directions to follow.

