#### **D.7.a Analyses to Test Specific Aims:**

The **primary specific aim** of this project is to examine if GCBT produces significant reductions in PTSD relative to the *SGP* condition and to determine if these changes are durable across a 12 -month follow-up interval. Two hypotheses will be tested.

**Hypothesis 1.** Patients with PTSD who receive GCBT will show greater reductions in PTSD-related symptoms relative to patients who receive *SGP*, at post-treatment assessment, a between-group difference that will persist through 6 month follow-up. To test this hypothesis, we will use multilevel latent growth modeling. Whereas a traditional latent growth model approach would suffice in many instances (e.g., when patients are treated individually), as noted earlier, the delivery of treatment in group format is likely to result in the violation of the assumption of independent observations (i.e., within-group similarity on treatment outcomes and process variables; cf. Schnurr et al., 2001, 2003). In initial analyses, we will evaluate the

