
***Hypothesis 2.*** Reductions in PTSD symptom severity will be maintained in the GCBT group at 12-month follow-up. Much as with Hypothesis 1, multilevel latent growth modeling will be used. In the analyses to examine Hypothesis 2, we will not include the treatment condition covariate but will include the site dummy code, to examine potential site differences. To test the prediction that the means of 6mos and 12mos do not differ, the slope factor loadings corresponding to these two time points will be constrained to equality and compared to the fit of a latent growth model where the 6 mo time point was freely estimated ( e.g., Baseline model:  $0^{* * 1}$ ; hypothesized model:  $0^{* * 1} 1$ ).

The **secondary aim** is to examine the generalizing effects of both GCBT and *SGP* on co-morbid conditions, distress and impairment. Because most trials in the PTSD literature do not include a thorough assessment of treatment generalization, it is unknown whether available treatments only address PTSD or whether gains generalize to related domains of functioning, including co-

morbid conditions such as depression, generalized anxiety, and alcohol use. Three hypotheses are proposed:

**Hypothesis 3.** For patients who are diagnosed with co-morbid Major Depressive Disorder (MDD), Generalized Anxiety Disorder (GAD), and/or Alcohol abuse prior to treatment, GCBT will produce significantly larger symptom reductions for these conditions, relative to SGP at post-treatment assessment and these generalized changes will show stability at 6 mo follow-up (FU). To test this hypothesis, we will use multi-level analysis, as discussed for Hypothesis 1. For continuous variables (BAI, BDI-II, SIP), we will use the same approach as described for Hypothesis 1. Although latent growth modeling can accommodate categorical outcomes (e.g., MDD+, MDD-) with an appropriate estimator (e.g., robust weighted least squares, maximum likelihood with numerical integration), there is concern about the estimation failure resulting from low cell frequencies, particularly at post-treatment and follow-up. In the event that cell frequencies are too low, we will augment the analyses from the continuous variables with more descriptively oriented statistics showing the rates of comorbidity decline at each assessment point as a function of treatment condition.

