### Protection against risk

We will carefully screen to identify individuals whose risk for potential adverse outcomes is elevated were they to participate in the proposed research. Such individuals will be excluded from the study. As an example, an actively suicidal person would be excluded from study participation and appropriate clinical care and referrals will be provided. The exact nature of "appropriate clinical care" will be determined by the judgment of clinicians and supervisors familiar with the specific participant and that person's access to community resources, and may include cognitive-behavioral treatment, other psychotherapy, referral to inpatient treatment or referral for medication treatment.

Clinical staff are trained to cope with any anxiety/distress experienced by participants during the assessments and treatment.

All personnel proposed for this project will have the required ethics, human subjects, and confidentiality training, which include information about maintaining data integrity and security.

Careful monitoring of participants during the pretreatment period and all phases of study participation will be conducted by the project staff. Each participant will see the same clinicians for each of their treatment visits. While waiting for a group to begin and during the follow-up interval, each participant will receive regular check-ins from the project coordinator. The project coordinator will be a Ph.D. level therapist who is trained to provide supportive services, as well as recognize if a participant is so distressed as to warrant exclusion from the trial. In particular, during the interval preceding the start of treatment as well as during the follow-up interval, the project coordinator will contact each participant once every 3-4 weeks, in order to determine how he is feeling and functioning (see below for further discussion of this choice). Veterans will be told to contact the project coordinator in case of emergencies or the respective VA after hours call line, which provides psychiatry on call service.

Explicit criterion for exclusion during the course of the trial are as follows:

1. Reporting of psychotic symptoms
2. Actively suicidal or homicidal (with intent)

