3. Displaying repeated disruptive behavior within the group treatment setting (examples include being sarcastic towards therapists or other group members, routinely arriving late by 30 minutes or more, hi-jacking the scheduled group content in order to direct attention to his own agenda). If there is a question about an individual's behavior during group, [name] will review the treatment recording and determine, in consultation with the other investigators on this application, if the veteran should be dropped from the trial.

Participants will be instructed to contact study personnel at any time (including during the follow-up interval) in the event of worsening of symptoms or relapse. Participants whose clinical condition has deteriorated will be removed from the study and given appropriate clinical care.

Participants failing to benefit from the study treatments will be provided with, or referred to, appropriate clinical care. Participants who begin treatment and experience adverse outcomes sufficient to require removal from the study will receive appropriate clinical care.

As in any type of treatment or clinical research program, participants' confidentiality must be carefully guarded and respected. All data with identifying information will be stored in locked files or password-protected computer files. Data being analyzed will be identified by subject codes, and identifying information will be removed. The identity of participants will not be revealed in the presentation or publication of any results from the project. All project staff will be educated about the importance of strictly respecting participants' rights to confidentiality and will have completed relevant training courses including proper practice in accordance with HIPAA regulations, protection of human subjects, and computer security.

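### The primary aim asks about durability relative to SGP across 12 months, but no GCBT-versus-SGP comparison of PTSD or SF-36 outcomes is specified beyond 6 months

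*Combined protocol and SAP*

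**What the plan says.** Sections A and D.7.a give the primary aim as testing whether GCBT reduces PTSD relative to SGP and "to determine if these changes are durable across a 12 -month follow-up interval".

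Two hypotheses serve that aim in D.7.a:
- H1 is comparative and claims "a between-group difference that will persist through 6 month follow-up". It is tested on CAPS total, and on PCL by the same method.
- H2 covers month 12 for one arm: "Reductions in PTSD symptom severity will be maintained in the GCBT group at 12-month follow-up". For its model, "we will not include the treatment condition covariate but will include the site dummy code". The test asks whether the 6- and 12-month means are equal.

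The secondary outcomes follow the same pattern. H4 (SF-36 subscales) is comparative to 6 months in D.7.a and to 3 months in Section A. H5 takes the GCBT group to 12 months by the H2 method. In D.7.d, diagnosis rates and reliable change by arm also end at 6 months.

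D.5 schedules assessments at 3, 6 and 12 months and explains that "it was important to demonstrate durability of changes following GCBT and SGP".

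**The concern.** A flat GCBT course from month 6 to month 12 does not show that GCBT remains better than SGP. Several influences in follow-up reach both arms. Under E.2, "the project coordinator will contact each participant once every 3-4 weeks", which is about 13 to 17 contacts a year (52/4 to 52/3), from a doctoral-level therapist trained in supportive work. Also, "Participants failing to benefit from the study treatments will be provided with, or referred to, appropriate clinical care". In the earlier VA group-therapy trial described in B.2, "Results indicated that patients in both treatment conditions showed improvements", with no difference between them.

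Only the randomised comparator can show whether GCBT's later course differs from what men assigned to SGP experience under the same conditions. Without it, the trial could report 12-month durability under a primary aim framed relative to SGP when the advantage has narrowed or gone. The outcome data needed to check this are already scheduled.

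**Working it through.** **1. Where each comparison ends (D.7.a and D.7.d)**

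| Analysis | Compared with SGP? | Last visit named |
|---|---|---|
| H1: CAPS, PCL | yes | 6 months |
| H2: PTSD severity | no, condition term removed | 12 months |
| H4: SF-36 subscales | yes | 6 months |
| H5: distress and impairment | no, H2 method | 12 months |
| Diagnosis, reliable change | shown by arm | 6 months |

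The general model description under H1 lets condition predict change over treatment and follow-up. It names no 12-month contrast, and H2 then removes the term.

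**2. The plan's own sample size**

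Inputs from the power section: d = 0.50, ICC 0.11, groups of 7, power 0.80, p < .05 (sidedness not stated; two-sided assumed).
- Unclustered n per arm = 2(1.960 + 0.842)²/0.50² = 62.8, so 63.
- Design effect = 1 + (7 − 1)(0.11) = 1.66.
- 63 × 1.66 = 104.6, so 105 per arm and 210 in total, against the stated 196.

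The figure of 196 does not reproduce two-sided at ICC 0.11. That is a separate matter, but it bears on the power in step 3.

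**3. Precision of the missing 12-month contrast**

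SE in SD units = √(2 × DE / n per arm), with DE = 1 + (m − 1)(0.11), where m is the mean number of men assessed per group. There are 14 groups per arm, so the t quantile on 26 df is 2.056. The retention rates are assumptions, because the plan gives none.

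| Retention | m | n per arm | DE | SE | 95% half-width | Power at d = 0.50, normal (t, 26 df) |
|---|---|---|---|---|---|---|
| 100% | 7 | 98 | 1.660 | 0.184 | 0.378 | 0.775 (0.744) |
| 80% | 5.6 | 78.4 | 1.506 | 0.196 | 0.403 | 0.723 (0.690) |
| 70% | 4.9 | 68.6 | 1.429 | 0.204 | 0.420 | 0.688 (0.655) |

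For a true d of 0.30 with no loss, power is 0.37 (normal). At the CAPS ICCs quoted in the power section (0.05 and 0.07), power at d = 0.50 with no loss is 0.866 and 0.836 (normal).

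**4. What H2 can and cannot detect**

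By arithmetic: start from a 0.50 SD advantage at 6 months and hold GCBT flat. If SGP improves by 0.3 SD, 0.50 − 0.30 = 0.20 SD remains. If it improves by 0.5 SD, nothing remains. H2 is met in both cases. The SGP improvements are illustrative; the documents give no late SGP course.

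By simulation: 4,000 runs per scenario, 14 groups of 7 per arm, ICC 0.11, no loss, 0.50 SD gap at 6 months and an assumed 6-to-12-month correlation of 0.7. A t-test on group means stands in for the latent growth model. Maintained means that the 6- versus 12-month GCBT difference is not significant.

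| Truth at 12 months | H2 maintained | Between-arm test significant |
|---|---|---|
| GCBT flat, gap 0.50 | 94.8% | 74.9% |
| GCBT flat, gap 0.25 | 94.9% | 25.6% |
| GCBT flat, gap 0 | 95.2% | 4.7% |
| Both arms worsen 0.3 SD, gap 0.50 | 20.8% | 75.3% |

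With GCBT flat, H2 passes about 95% of the time whatever has happened to the advantage. When the advantage is intact but both arms drift, it mostly fails.

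**The case against.** The best defence is that H2 does what it says. Section A, D.4 and D.7.a all word the 12-month hypothesis as maintenance in the GCBT group, and the analysis matches. A comparative test to 6 months followed by within-arm maintenance is a coherent sequence if the changes in the primary aim are read as GCBT's own reductions. This stands as a defence of H2. It does not supply a comparison for an aim whose first half is explicitly relative to SGP.

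A reader might infer more than the documents support:

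- **That SGP data are excluded at 12 months.** H2 removes the condition covariate; it does not say whose data enter. A GCBT-only model is the natural reading, but the missing-data text under the analytic approach says every analysis keeps all 196 men. On that reading the arms are pooled. Neither reading gives a comparison.
- **That durability against control is not tested at all.** H1 tests it to 6 months. The gap is months 6 to 12.
- **That SGP's 12-month data go wholly unused.** They may enter the fallback comorbidity rates by arm under H3 and the utilization models in D.7.d, which set no 6-month limit.
- **That a 12-month contrast would isolate GCBT from later care.** It would not. Men in either arm may be referred onward, and unequal referral could shrink or widen the difference.

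The limited power is also a fair objection. If significance were the rule, a fully kept 0.50 SD advantage would be missed in roughly a quarter of trials even with complete data.

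**Conclusion.** The point holds in this form: no 12-month GCBT-versus-SGP contrast is specified for CAPS, PCL or the SF-36 outcomes, so durability relative to SGP is tested only to 6 months. H2 and H5 cannot fill the gap, because their result does not depend on what happens in SGP.

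The size of any lost advantage is unknown. The fall from 0.50 to 0.20 or 0.00 SD shows what H2 would miss and is not a forecast. The precision figures rest on ICC 0.11, equal groups, an unadjusted difference and, for 0.40 to 0.42 SD, an assumed 20 to 30% missing. The conclusion about H2 follows from its wording and needs none of these values. The mismatch with the primary aim assumes that the aim's durability clause refers to the reductions relative to SGP.

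**What to change.** In D.7.a (H2 and H5):

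1. Keep both arms and the condition term in a model that includes the 12-month visit.
2. Report the GCBT-minus-SGP difference at 12 months with its 95% CI for CAPS total and the H5 outcomes, and for PCL by the method it shares with CAPS.
3. Base any statement of durable benefit relative to SGP on that estimate.
4. Keep the H2 and H5 tests, labelled as within-arm maintenance, and say which men enter them.

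In D.7.d, extend the diagnosis and reliable-change summaries by arm to 12 months.

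The cost is analysis wording, since the 12-month assessments are already scheduled in both arms. The downside is a harder standard with limited power (about 0.78 at d = 0.50 with no loss, lower with attrition), so the estimate and CI should carry the message. The report should also say that the contrast reflects assigned treatment plus any later care. The monthly records in D.4 should not be relied on to identify later PTSD treatment: they are described as counts of medical visits, with no mention of visit type.

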In addition to statistical significance, we were concerned about the potential clinical significance of these data. Presently, there is no agreed-upon effect size that is thought to be clinically significant. This is difficult to determine because effect sizes hinge on many variables (e.g., the size and nature of the sample, the amount of variance in the assessment strategy, the amount of variance in treatment administration). In our power calculations, we have relied on a .80 power level, to have a sufficient sample size for this RCT for statistical significance. Unfortunately, there is no consensus in the treatment literature regarding what constitutes a clinically significant effect size; Friedman and colleagues (2006) suggest that clinically meaningful differences between 2 active treatments would be illustrated by an effect equal to or greater than .30 (Cohen's  $d$ ). Consultation with [name] (Project Statistician) thus indicates that the proposed  $n$  will be sufficient to determine whether GCBT produces clinically meaningful outcomes.

**Analytic approach:** Data from both sites will be combined prior to analyses. [name], the Project Statistician, will work in close collaboration with [name] to perform the analyses. Prior to testing hypotheses, the outcome data will be examined to assess if they meet the assumptions for the proposed statistics (Tabachnick & Fidell, 2001). If the assumptions are not met (e.g., the data depart from normality, multivariate outliers are present), appropriate data transformations will be used. Additionally, the GCBT and SGP groups will be examined for pre-treatment differences, to test for group equivalency. These analyses will involve a series of independent  $t$ -tests on each of the outcome measures as well as demographic variables. Pre-treatment differences between conditions will be incorporated into the models used to examine the primary hypotheses, as described below.

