extent of dependency (i.e., clustering) by calculation of intraclass correlations (ICCs) using variance estimates from unconditional cell means models of key outcome variables (cluster = treatment group). Our proposed  $N$  of 196 will be clustered into 14 treatment groups per condition. Assuming non-zero ICCs, a multilevel approach will be incorporated into the latent growth framework in order to obtain correct standard errors, test statistics, and confidence intervals. In the traditional multilevel modeling, the design would be construed as a three-level model; i.e., repeated observations (Level 1) nested under individuals (Level 2), individuals nested under treatment groups (Level 3). However, because the first two levels are combined in the multivariate framework of latent growth modeling, this design can be characterized as a two-level model (i.e., latent growth factors are nested under treatment groups) where time-invariant covariates (i.e., dummy codes for treatment condition) are included to account for the within-group and between-group variability in initial status (pre-treatment) and symptom change (improvement over active treatment and follow-up). In the latent growth model portion of the models, the intercept will be centered on pre-treatment (i.e., first slope loading will be fixed to 0.0). Because there is no substantive interest in the form of the growth trajectory, intermittent time points (i.e., slope factor loadings) will be freely estimated and the final timepoint of interest (e.g., post-treatment) will have a corresponding factor loading fixed to 1.0. Accordingly, the mean and variance of the slope will convey the fixed (average) and random effects (individual differences) of change for the given time interval of interest. The Level 2 variables of treatment condition (single dummy code using *SGP* as reference group) will be included as predictors to account for individual differences in treatment response and variability in outcome across treatment groups. To examine pre-treatment differences between treatment conditions, the intercept (centered on pre-treatment) will be regressed onto the treatment covariates (i.e., significant paths are indicative of differences in pre-treatment levels as a function of treatment condition). Any pre-treatment differences will be accommodated into the interpretation of findings and in the parameterization of the models (e.g., regression of the slope onto the intercept, as well as covariates such as treatment condition). The dependent variable for this analysis is the CAPS total score. Additionally, PCL will be examined, using the same analytic approach, in order to examine respondent effects (interviewer-rated versus self-report).

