**Hypothesis 4.** Patients who receive GCBT will report less distress and impairment, relative to patients who receive SGP, at post-treatment assessment, a between-group difference that will persist through 6 month follow-up. To test this hypothesis, we will use multi-level analysis, as discussed for Hypothesis 1. For continuous variables (SF-36 subscales), we will use the same approach as described for Hypothesis 1.

**Hypothesis 5.** Gains in these domains (distress and impairment) will be maintained in the GCBT group at 12-month follow-up. To test this hypothesis, we will use multilevel latent growth modeling, using the same approach as discussed for Hypothesis 2.

**D.7.d. Secondary data analyses:** In addition to analyses designed to test these hypotheses, several secondary analyses will be conducted. **(1). Diagnostic and reliable change status:** In order to facilitate comparison with other RCTs, we will compute the percentage diagnosed with PTSD for both GCBT and SGP at post-treatment and , 3- and 6- mo follow-up. To determine reliable change, we will follow guidelines outlined by Jacobson and Truax (1991). Specifically, the reliable change index utilizes both the reliability of measurement device, along with a confidence interval, to determine reliable change. We will utilize CAPS Total scores and a stringent confidence interval (95%) to determine reliable change scores within both the GCBT and SGP conditions, at post-treatment and 6 mo follow-up assessment.

**(2). Examine the generalizing effects of both GCBT and SGP on healthcare utilization.** We will examine the effect of PTSD group treatment on healthcare utilization. We expect that veterans who receive GCBT will display less health care utilization relative to veterans who receive SGP. We will use the same multilevel analysis approach described above (with number of health care visits as the continuous variable).

**(3). Predictors of individual differences in outcome:** Although the primary aims of this RCT do not include a focus on individual differences that may affect outcome, we propose analyses to look at select variables in this regard. Recognizing that these are exploratory, we propose to look at (1) the number of sessions attended, (2) group psychotherapy alliance (four

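### Hypotheses 2 and 5 judge maintenance only from 6 to 12 months and without a margin, so gain lost before 6 months cannot count against it

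*Combined protocol and SAP*

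**What the plan says.** Durability is part of the primary specific aim: the trial is to "determine if these changes are durable across a" 12-month follow-up (D.7.a). Hypothesis 2 reads "Reductions in PTSD symptom severity will be maintained in the GCBT group at 12-month follow-up".

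The test under Hypothesis 2 is brief. "To test the prediction that the means of 6mos and 12mos do not differ", the loadings for those two occasions are set equal, and the fit is compared with that of a model in which the 6-month loading is free. For this model, "we will not include the treatment condition covariate but will include the site dummy code". Hypothesis 5, on distress and impairment, is tested "using the same approach as discussed for Hypothesis 2".

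The growth model itself is described under Hypothesis 1. The pre-treatment loading is 0, the last occasion of interest has loading 1, and those between are estimated freely, so that "the mean and variance of the slope will convey the fixed (average) and random effects (individual differences) of change".

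In D.7.a, Hypotheses 1 and 4 run to 6 months, as differences between arms. D.7.d adds PTSD diagnosis rates at post-treatment, 3 and 6 months, and reliable change "at post-treatment and 6 mo follow-up assessment". The plan gives no maintenance margin, no fraction of gain to be retained, no rule for reading the fit comparison, and no power figure for Hypothesis 2 or 5.

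**The concern.** A claim that a reduction has been maintained at 12 months compares 12 months with the point where the reduction was achieved, the end of treatment. The stated test starts at 6 months. Whatever was lost between post-treatment and 6 months lies outside it.

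The prediction is also a null hypothesis. Without a margin, the natural reading is that non-significant misfit supports it. Few men, dropout or clustering then make maintenance easier to claim.

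A smaller point is that the text drops the treatment term without saying that the model is fitted in the GCBT arm only. Taken literally, that would pool both arms.

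At stake is the durability half of the primary aim, and the matching claim for distress and impairment.

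**Working it through.** The plan has no figure of its own to reproduce here: its 196 is the sample size for the between-arm contrast. The check has three steps.

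**1. What the comparison can see.** Write the mean at occasion t as α + λₜμ, with λ = 0 at pre-treatment and λ = 1 at 12 months. The constrained model sets λ₆ = 1 and the comparison model frees λ₆. The mid-treatment, post-treatment and 3-month loadings are free in both. Suppose the gain is G at post-treatment, G/2 at 6 months and G/2 at 12 months. Then μ = −G/2, λ_post = 2 and λ₆ = 1. The constraint is exactly true, so a 5% test passes in about 1 − 0.05 = 95% of trials whatever λ_post is. Complete relapse would at least appear as a slope mean near zero. Partial loss leaves a clear change from pre-treatment.

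**2. Simulation of the planned comparison.** Assumptions: one arm, six occasions, intercept variance .6, slope variance .25, residual variance .4 (pre-treatment SD 1; 6–12 month correlation about .62–.68), no clustering. Method: maximum likelihood, likelihood-ratio test of λ₆ = 1 at 5%, 1000 trials per cell. The 95% Monte Carlo error near the 95% pass rates is 1.96·√(.95·.05/1000) ≈ 1.4 points. The gain of 1.35 SD is the pilot pre-to-post effect on the PCL-M (C.2). The 69 men are 98 less 30% (98 × .70 = 68.6).

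| True course | Passes, n = 98 | Passes, n = 69 |
|---|---|---|
| All gain kept | .951 | .949 |
| Half lost by 6 months, then flat; gain 1.0 SD | .946 | .944 |
| Half lost by 6 months, then flat; gain 1.35 SD | .948 | .943 |
| 0.20 SD worsening from 6 to 12 months | .358 | .508 |

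In the half-lost trials the pre-to-12-month change was still significant in 99–100%.

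A second simulation used other variances (intercept SD .75, residual SD .6, slope SD half the mean 12-month change; n = 98; gain 1.0 SD; 200 trials per cell, standard error about 2 points). The planned test passed in 93% with all gain kept, 92% with half lost and 94.5% with three quarters lost. A direct paired test of post-treatment against 12 months detected the loss in 100% of trials in both loss scenarios.

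**3. Absence of a margin.** As a paired complete-case approximation in SD units, with 14 GCBT groups:

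SE = √(2(1 − r)) · √((1 + (n/14 − 1)·ICC)/n)

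Probability of missing a 0.20 SD worsening = 1 − Φ(0.20/SE − 1.96)

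- n = 98, r = .8, ICC 0: SE = .632 × .101 = .064; missed in 12%.
- n = 98, r = .5, ICC .11: SE = √(1.66/98) = .130; missed in 66%.
- n = 69, r = .5, ICC .11: SE = √(1.432/69) = .144; missed in 72%.

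The ICC of .11 is the value in the plan's power calculation. The correlations, the use of that ICC for change scores and the 30% loss are assumptions; the documents give none of them.

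**The case against.** The strongest reply is that the planned model would show an early loss. With half the gain lost, the free post-treatment loading is about 2. In refits under the first set of variances its median was 1.97 (n = 98) and 2.00 (n = 69), and its Wald interval excluded 1 in every trial. That is true, and a careful analyst would notice. But no stated rule uses that loading, so the decision on Hypothesis 2 or 5 does not depend on it.

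Second, Hypothesis 1 (and Hypothesis 4 for distress and impairment) covers the period to 6 months, so the hypotheses can be read as consecutive intervals. They are between-arm contrasts, however. A difference from SGP can persist while GCBT loses gain, provided SGP loses gain too. The D.7.d rates give partial warning, but they stop at 6 months and do not gate either hypothesis.

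Third, the 94–95% pass rate follows by construction, because the constraint is true. That is correct. The simulation confirms the algebra; it does not estimate how often the whole trial would mislead.

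Fourth, the miss rates rest on assumed inputs. The worst cases use complete cases, whereas the plan retains partial data by direct maximum likelihood, and .11 exceeds the CAPS values of .07 and .05 that the plan reports. This also stands, and is why a range is given.

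Fifth, Hypothesis 2 names the GCBT group, so a single-arm fit is the likely intention. The missing statement is only a matter of wording. The printed loading patterns are hard to read, so the reading here rests on the sentence describing the test.

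**Conclusion.** The concern holds and should be fixed. The stated comparison passes about equally often, near 95%, whether men keep all of their gain or only half. It therefore cannot by itself support a claim of durability over 12 months. This conclusion follows from the structure of the test and needs no assumed variance.

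The lack of a margin is a second weakness, whose size does depend on assumptions. A true 0.20 SD worsening after 6 months is missed in 36–51% of trials in the first simulation, and in 12–72% on the paired approximation (r .5–.8, ICC of change 0–.11, 0–30% loss). It also presumes that non-significance is to be read as support, which the plan does not say outright.

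The Hypothesis 1 treatment contrast is untouched.

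**What to change.** - State that the Hypothesis 2 and 5 models are fitted in the GCBT arm.
- Make post-treatment versus 12 months the maintenance contrast. Keep 6 versus 12 months as secondary, and report the pre-treatment to 12-month change alongside.
- Conclude maintenance only if the two-sided 95% confidence limit for mean worsening, in each scale's worse direction, lies below a margin the sponsor justifies in advance. Otherwise report the change with its interval and make no maintenance claim.
- Apply the same rule to Hypothesis 5.

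The paragraph on clinical significance after the power calculation cites a suggestion that "clinically meaningful differences between 2 active treatments would be illustrated by an effect equal to or greater than .30" (Cohen's d). That figure concerns differences between treatments, so it is at most a starting point for a margin.

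The cost is SAP wording; the assessments are already scheduled. The claim becomes harder to obtain. With an illustrative margin of .30 SD, no true change and ICC .11, power is Φ(.30/SE − 1.96), where r is now the post-treatment to 12-month correlation:

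| Men | r = .3 | r = .5 | r = .8 |
|---|---|---|---|
| 98 | .495 | .635 | .954 |
| 78 | .447 | .580 | .927 |
| 69 | – | .549 | .909 |

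In the first simulation (no clustering), this rule declared maintenance in at most 0.1% of half-lost trials. With all gain kept it did so in 89.6% (n = 98) and 77.4% (n = 69).
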